## 9.7. Expected Duration of Study

The total study duration for a given participant will be 26 weeks. Week 0 will comprise the baseline assessment and LiOR initiation will occur as soon as feasible after this. Intermediary assessments will be conducted at week 2, week 4, week 8 and week 16, followed by the final follow-up assessment and discontinuation of LiOR at week 26. The beginning of the study overall will be Week 0 (baseline assessment) of the 1st participant, estimated October 2024, and the end of the study will be one month after the last week of the 40th participant's follow-up assessment, estimated to be in August 2025, to allow for sample analysis.

# 10. Study Procedures

#### 10.1. By Visit

The summary table in section 6.3 describes the procedures at each 'visit' (or measurement timepoint) which are also described below. We refer to each timepoint by its week number (W), (except for the first screening, which is not assigned a 'W' timepoint).

Once identified through different recruitment sources, potential participants will be first contacted regarding the study by a researcher who will send them a copy of the Participant Information Sheet (PIS; via email, post or in person). The researcher will encourage potential participants to spend as much time as they need asking questions about the study (via email or phone call) and consider whether they wish to participate or not.

As a minimum, study information will be provided to potential participants at least 24 hours prior to screening. After reading the PIS and having any questions answered, if the participant is happy to take part in the study, an appointment for screening will be arranged.

An alternative option to above is that participants will be provided with a link to a Qualtrics pre-screening questionnaire. The first page seen, if participants choose to follow this link, is the PIS. If participants confirm that they have read this, they are invited to either give preliminary consent to undertake the initial screening questionnaire, or contact the study team to discuss further (as in above route). If they select to complete the initial

screening questionnaire, this comprises questions which can be used to quickly exclude ineligible participants (e.g., age, health status, medication status) and the ISS to indicate whether they may be experiencing depression with mixed features. If participants are not indicated to be ineligible from this questionnaire, they can select for the study team to be contacted with their results and to establish further contact and potentially progress to full screening.

#### Screening session

Usually conducted over the phone by a trained researcher, or if potential participants are willing, by videocall (i.e., King's College London MS Teams) study information will be discussed and verbal consent for screening obtained. Verbal consent for screening will be recorded in a secure, password-protected spreadsheet for all potential participants. If the potential participant is willing, screening will provide an initial determination of eligibility. Specifically, eligibility will be assessed via screening procedures as follows:

- Open questions for self-report:
  - Eligible age range.
  - Willingness to try a commercially available lithium supplement.
  - Clinical health diagnoses (including bipolar disorder).
  - Severity of any diagnoses [participants are excluded if admitted to hospital within the past 6 months, have a planned admission in the upcoming 6 months, or attend outpatient/secondary services for an illness other than an affective disorder at least once per month].
  - Current treatments undergone for depression [name(s) of current medication, initiation / withdrawal and historical dose changes].
  - Ineligibility for lithium [as above; taking lithium, known cardiac disease or insufficiency, renal impairment, untreated thyroid dysfunction, breastfeeding, pregnancy, hyponatraemia, dehydration, regular use of NSAID, ACEI or diuretics, psoriasis, Addison's disease, Brugada syndrome or family history of Brugada.]
  - Ability to travel to one of the research sites on a regular basis over 6 months.
- MINI interview, MDD module, to establish current depressive episode and suicide module to establish nonsignificant suicide risk.
- (if not completed within Qualtrics within the last week), Internal States Scale [ISS] to establish presence of mixed features within current depressive episode.
- Ability to communicate fluently in English: researcher-defined, via ability to communicate during discussions about understanding of participant information and prior questions.
- Ability to provide informed consent to participate: researcher-defined, via communications and understanding of the procedures being consented to.

If inclusion criteria are met following this, the W0 assessment will be scheduled.

All assessments are expected to take place in the morning, as (post-LiOR initiation), blood samples are taken in the morning, at least 12 hours after the last LiOR dose, to avoid acute effects of lithium intake.

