#### 7.4. Concomitant treatments (usual care)

All participants will continue receiving TAU including all concomitant interventions and service use. We will monitor and record these. In addition to monitoring at each assessment, participants are asked to inform the team immediately of any new intervention they have been prescribed and/or are considering initiating, to ensure these have no potential contraindications with the study supplement.

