#### 9.2. Exclusion Criteria

People meeting any of the following criteria will be excluded:

1) Clinical diagnosis of bipolar disorder.

2) Other health condition that is severely impairing (as per self-report).

3) Known contraindication to lithium treatment. This includes currently taking lithium. These are derived from those applicable to medically prescribed forms of lithium. Although these are not established contraindications to microdoses of lithium, we are including them to fully ensure no ill effects to our study participants. These include:

- Known allergy to lithium or its excipients
- Known cardiac disease or cardiac insufficiency
- Known renal impairment
- Known untreated thyroid dysfunction
- Breast-feeding or pregnant
- Known hyponatraemia or frequent dehydration
- Addison's disease

- Brugada syndrome or family history of Brugada syndrome
- Psoriasis
- Upcoming use of, unable or unwilling to abstain from using any of the following medications during the upcoming 6 months:

- non-steroidal anti-inflammatory drugs (NSAID) or cyclo-oxygenase-2inhibitors i.e., aceclofenac, acemetacin, celecoxib, dexibuprofen, dexketoprofen, diclofenac, diflunisal, etodolac, etoricoxib, fenbufen, fenoprofen, flurbiprofen, ibuprofen, indomethacin, ketoprofen, lumiracoxib, mefenamic acid, meloxicam, nabumetone, naproxen, piroxicam, sulindac, tenoxicam, tiaprofenic acid, ketorolac, metronidazole.

- angiotensin-converting enzyme inhibitors (ACEI) i.e., captopril, cilazapril, enalapril, fosinopril, imidapril, lisinopril, moexipril, perindopril, quinapril, ramipril, trandolapril.

- Angiotensin receptor blockers (ARBs) i.e., azilsartan, candesartan, irbesartan, losartan, Olmesartan, telmisartan, valsartan.

- diuretics i.e., Bendroflumethiazide, chlortalidone, cyclopenthiazide, indapamide, metolazone, xipamide, bumetanide, furosemide, torasemide.

It is worth noting that several other medications can interact with lithium e.g., steroids or reduced lithium levels from e.g., empagliflozin, aminophylline, theophylline. However, these are not included in guidelines as contraindicatory for high-dose lithium and are not included in exclusion criteria.

4) Unable to communicate fluently in English (defined as ability to read and understand the participant information sheet plus ability to communicate with the researcher throughout screening assessment);

5) Suicide risk (assessed using the MINI)

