#### Sociodemographic/illness-history/service use questions

- Date of birth, gender, ethnicity, height, weight, education level (highest level of education), employment status, substance use (e.g., smoking, alcohol), stressful life events within the past 12 months [baseline only]
- Current health symptoms [week 0 and 26]
- Current pharmacological or other medical treatments (type, dose, frequency of use, duration of use) [all timepoints]
- Previous use of lithium [baseline only]
- Use of healthcare and related services [week 0 and 26]
- Psychiatric comorbidities (questions) [week 0 and 26]
- Bipolar risk measures (questions; MINI bipolar section, HCL, TEMPS) [week 0 and 26]

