#### Wellbeing measures

- Low mood: The Maudsley 3-item visual analogue scale (M3VAS) and investigator-rated Inventory of Depressive Symptoms (IDS) [all timepoints]
- Anxiety: The Generalised Anxiety Disorder 7-item scale (GAD7) [all timepoints]
- Elevated mood: The internal states scale (ISS) and investigator rated Young Mania Rating Scale (YMRS) [all timepoints]
- Functional/wellbeing measures [EQ5D[week 0 and 26], FAST[all timepoints]]

Participants will, at the end of the assessment, be provided with one pot containing 60 LiOR capsules (for weeks 0 to 2). They will also be provided with an information sheet regarding LiOr, and instructed to begin taking the supplement the next day and once each day thereafter.

The researcher will offer two aids to help participants remember to take the supplement: participants can choose to receive a daily text message from the team to remind them to take their daily LiOR, or they can (along with the researcher if desired) set themselves an alarm/reminder for themselves.

The researcher will subsequently send a letter of notification regarding the study (and information about LiOR) to the participants' named Healthcare Professional.

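### Pregnancy and breast-feeding exclude entry, but the protocol lists no targeted question after remote screening and no rule to stop LiOr, report a pregnancy or follow its outcome

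*Protocol*

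**What the plan says.** Section 9.2, item 3, lists pregnancy and breast-feeding among the contraindications to lithium, with renal, cardiac, thyroid and sodium conditions and several drug classes. It gives the reason: "Although these are not established contraindications to microdoses of lithium, we are including them to fully ensure no ill effects to our study participants".

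Section 10.1 (Screening session) asks about the list by self-report: "Ineligibility for lithium [as above; taking lithium, known cardiac disease or insufficiency, renal impairment, untreated thyroid dysfunction, breastfeeding, pregnancy, hyponatraemia". Section 8 makes this session remote, and Table 1 marks the eligibility assessment under Screening only. The text says that "screening will provide an initial determination of eligibility", but describes no later determination.

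At W0 the protocol lists consent, bloods and questionnaires, including "Current health symptoms [week 0 and 26". Participants then "be provided with one pot containing 60 LiOR capsules (for weeks 0 to 2". The named healthcare professional is told afterwards: "The researcher will subsequently send a letter of notification regarding the study (and information about LiOR) to the participants".

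Drug contraindications are followed during dosing. Section 7.4 states that "participants are asked to inform the team immediately of any new intervention they have been prescribed and/or are considering initiating", and section 10.1 records "Current pharmacological or other medical treatments (type, dose, frequency of use, duration of use) [all timepoints".

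**The concern.** The drug and non-drug contraindications sit in the same exclusion item. The protocol keeps the drug part under review for 26 weeks. Pregnancy and breast-feeding can also begin within 26 weeks, yet the protocol states no equivalent check and no action if one is found.

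Followed as written, a participant who becomes pregnant after screening and does not mention it could keep receiving lithium capsules by post. The protocol counts a congenital anomaly as a serious adverse event, but that criterion cannot stop exposure, and the birth would normally come after the participant's last planned contact.

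**Working it through.** **Inputs.** Contacts: screening, then W0, 2, 4, 8, 16 and 26 (section 9.7). One pot holds 60 capsules of 5 mg (section 7.1). LiOr starts the day after W0 and ends at W26 (sections 7.2 and 9.7). Assumptions not in the protocol: 38 weeks from conception to term, and one pot per delivery.

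**Stated supply figure.** 20 mg is 4 capsules a day; 60 / 4 = 15 days per pot, which matches section 7.1.

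**What each contact lists.**

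| Contact | Listed content bearing on this point | Targeted pregnancy or breast-feeding question |
|---|---|---|
| Screening (remote) | Lithium contraindication list, self-report | Yes |
| W0, before dispensing | Health symptoms, service use, treatments, bloods | None listed |
| W2, W4, W8, W16 | Treatments, bloods, general adverse-event questions | None listed |
| Postal re-supply | Remaining quantity | None listed |
| W26 | Health symptoms, service use, treatments, bloods | None listed; LiOr ends here |

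The targeted question is therefore listed at 1 of 7 scheduled contacts; treatments are recorded at all 6 from W0.

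**Blood tests.** Sections 10.1 and 10.2 name lithium, inflammatory markers and growth factors. Table 1 also marks a screening blood test, and section 11.1 mentions clinical blood tests, but neither is described further. No pregnancy test is named.

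**Longest stretch without the question.**
- As written: 26 × 7 = 182 days from W0 to W26, plus the screening-to-W0 interval, which is not given.
- Asked at W0 to W16: the gaps between visits are 14, 14, 28, 56 and 70 days; the longest is (26 − 16) × 7 = 70 days, ending when LiOr ends.
- Asked at re-supply as well: 60/4 = 15 days at 20 mg, 60/3 = 20 at 15 mg, 60/2 = 30 at 10 mg, 60/1 = 60 at 5 mg.

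**Supply outside visits.** At 20 mg, 182 × 4 = 728 capsules, and 728 / 60 = 12.1, so 13 whole pots. If two are handed over in person (weeks 0 to 2 and 2 to 4) and the rest posted, about 11 go by post. Between W16 and W26, 70 / 15 = 4.7 pots are used with no visit.

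**Birth timing.** Conceived just after W0: 38 − 26 = 12 weeks after W26. Conceived at W26: 38 weeks after. Section 9.7 ends the study one month after the last participant's follow-up.

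**Actions in section 11.** Section 11.1 fixes actions for abnormal bloods, lithium above 0.6 mmol/L, more than half of participants wanting a lower dose, and wellbeing concerns. Section 11.3 requires LiOr withdrawal for serious adverse reactions and SUSARs. None of 11.1 to 11.5 names pregnancy as a reason to stop or report, or provides for following its outcome.

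**The case against.** The strongest reply is that the protocol is not silent in practice. Under section 11.2 the researcher checks verbally for negative effects and records notable events, passing concerns to the Lead Investigator and medical expert. Section 11.3 adds a general question at every visit. Health symptoms and service use are asked at W0 and W26, the healthcare professional is notified, and section 9.6 lets the investigator withdraw anyone. A disclosed pregnancy would plausibly be acted on. That stands, but a wanted or early pregnancy need not be raised as a trouble or a negative effect, service use is not asked between W0 and W26, and postal deliveries fall outside the visits.

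A reader might infer that all the non-drug contraindications go unchecked for 182 days. The documents do not support that. Serum lithium is measured at each visit from W2, and a level above 0.6 mmol/L lowers the maximum dose to 10 mg (section 11.1). This partly covers renal, dehydration and sodium problems, which matter mainly by raising the level. A new cardiac, renal or thyroid diagnosis would also often bring a new treatment, which must be notified and is recorded at every visit. These items are secondary.

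The interval counts also give the general prompts no value, and a question at W26 cannot shorten exposure. The information sheets and case report form are not shown and may carry pregnancy advice or a check; if so, the protocol does not say so. Finally, another self-report question still misses a pregnancy the participant has not recognised.

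**Conclusion.** The point holds for pregnancy and breast-feeding. The protocol excludes both, lists a targeted question only at remote screening, and gives no rule to stop LiOr, report a pregnancy or follow its outcome. The gain available is from an open prompt to a targeted one with a defined action, not from no safeguard to a safeguard.

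In size, up to 182 days of dosing run without the question, reducible to 70 days through visits and to about 15 days at 20 mg through re-supply contacts. A term birth conceived on LiOr would come about 12 to 38 weeks after W26. These figures rest on the scheduled visit weeks, one pot per delivery and 38 weeks to term.

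It would be wrong to infer that LiOr at this dose is shown to harm a pregnancy, or that cases are expected. Section 9.2 calls the list precautionary at microdoses, and the protocol gives no sex mix or pregnancy rate. The number among 40 people is likely to be small. No co-primary outcome or sample-size statement is affected. The amendment is worth making because it is cheap and carries the protocol's own precaution through the dosing period.

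**What to change.** - At W0 before dispensing, at W2 to W16 and at each re-supply contact, ask and record whether the participant is or might be pregnant, or is breast-feeding. Optionally ask in the same breath about any new renal, cardiac, thyroid or sodium diagnosis.
- On a positive answer, stop supply, advise the participant to stop the capsules already held, and inform the medical expert through the section 11.2 route.
- Ask once more at W26, to identify exposed pregnancies.
- Add to section 11.3 that any pregnancy on LiOr is reported and its outcome followed, with consent, beyond W26.

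Cost: a few minutes at contacts already planned, a protocol amendment, consent wording for the longer follow-up, and, for a rare case, follow-up that may run past study end. No extra visit or test is needed, but unrecognised pregnancies would still be missed.

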## 8. Research environment

The study will take place in one location. The Clinical Research Facility (CRF) at King's College Hospital will be used for all study procedures (blood tests, interviews and questionnaires), but the screening assessment will be conducted via telephone/videocall. The CRF is a purpose-built facility to support clinical trials and provides ideal infrastructure for studies of this nature (biological testing and processing facilities, quiet, private rooms with appropriate space for testing materials).

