## 11. Assessment of Safety

#### 11.1. Assessment of Therapy Safety

Safety is not an outcome of this study, as the supplement has been evidenced to be safe (having been available and used without supervision, in the community, for decades). However, the welfare of our participants is paramount, and we will closely monitor information obtained from participants to ensure their safety. Specifically, this includes monitoring of lithium levels and wellbeing measures (as soon as each information are available to the research team). Monitoring and proposed actions comprise:

- a. If any abnormalities are noted from clinical blood tests, participants and their GPs will be informed within one working day by study researchers. NB these are likely to be incidental, not associated with the intervention, given evidence to date of safety.
- b. If any lithium levels exceed 0.6mmol/L, the dosing regime will be lowered from 20mg to 10mg as maximum dose as soon as practicable. This would be highly unexpected, given that the typical dose of lithium carbonate required to achieve therapeutic levels (0.6-0.8mmol/L) is 600-800 (approximately 6-8 times the elemental equivalent in LiOR 20mg).
- c. If >50% participants (at any point in time) report a desire to reduce from 20mg, the dosing regimen will be lowered from 20mg to 10mg as soon as practicable.
- d. If any wellbeing concerns arise in general, participants will be contacted within one working day by a study researcher for a wellbeing discussion and to provide support (i.e., study-related actions, signposting e.g., to support or healthcare services).

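### The 10.1 screening list and the Table 1 screening blood test do not match the exclusions in 9.2 or the consent sequence

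*Protocol*

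**What the plan says.** **Exclusions.** Protocol section 9.2 lists contraindications to lithium, among them an allergy to lithium or its excipients. For four groups of medicines (NSAIDs including COX-2 inhibitors, ACE inhibitors, ARBs and diuretics) the rule is "Upcoming use of, unable or unwilling to abstain from using any of the following medications during the upcoming 6 months". ARBs have their own entry: "Angiotensin receptor blockers (ARBs) i.e., azilsartan, candesartan, irbesartan, losartan, Olmesartan, telmisartan, valsartan".

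**Screening list.** The screening session in section 10.1 sets out what potential participants are asked. The item on ineligibility for lithium opens with a reference back to the exclusions and then gives its own list, which includes "hyponatraemia, dehydration, regular use of NSAID, ACEI or diuretics, psoriasis". If the criteria are met, the W0 visit is scheduled.

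**Blood test and consent.** Table 1 (section 6.3) marks the blood-test row in all four columns, including Screening, and places informed consent at Baseline. Section 8 says that "the screening assessment will be conducted via telephone/videocall". Section 10.1 has verbal consent for screening and written consent at the start of W0, and the first blood sample it describes is at W0.

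**Suicide criterion.** Section 9.2 has "Suicide risk (assessed using the MINI" with no level stated. Section 10.1 has "suicide module to establish nonsignificant suicide risk". The synopsis likewise excludes only significant suicidality.

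**The concern.** Section 9.2 says that the contraindications were taken over from prescribed lithium as a precaution, to protect participants. They rest largely on self-report, so they work only if the screening questions ask for the same things. If the operational list is shorter than the formal one, or sets a different threshold, two screeners can reach different decisions on the same person, and one of those decisions breaches 9.2.

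The blood-test mark raises a consent question. Read literally, Table 1 calls for a blood sample at a stage when the participant is on the telephone or a videocall and has given verbal consent only.

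**Working it through.** No arithmetic applies. The check sets the passages side by side.

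**1. Section 9.2 against the 10.1 list**

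| Item | Section 9.2 | Section 10.1 screening list |
|---|---|---|
| Currently taking lithium; cardiac, renal and untreated thyroid disease; pregnancy and breast-feeding; hyponatraemia and dehydration; Addison's; Brugada; psoriasis | Excluded | Present |
| Allergy to lithium or excipients | Excluded | Absent |
| NSAIDs, ACE inhibitors, diuretics | Excluded | Present |
| ARBs | Excluded | Absent |
| Use threshold for the medicines | Expected use, or unable or unwilling to abstain, over six months | Regular use |

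One of four drug classes and one non-drug contraindication are therefore missing from the itemised list.

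The threshold differs as well. Take a person who uses an NSAID now and then and is unwilling to stop for six months. That person meets the 9.2 exclusion, but is not a regular user and so passes the 10.1 item as written.

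**2. Is there a later step that would catch this?** Section 10.1 records current medication at W0, which could bring an ARB to light. It does not call this an eligibility step, and no re-check of the criteria at W0 is described. No later question about allergy is described either.

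**3. Table 1 against the text**

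- Table 1: blood test at Screening, W0, intermediary visits and W26; informed consent at Baseline.
- Section 8 and the 10.1 screening session: remote contact, verbal consent, no blood sample listed.
- Section 10.1, W0: written consent first, then the blood test.

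The opening of 10.1 says that the visit text describes the procedures in Table 1, so the two are meant to agree. The row has a mark in each of four columns, so a column shift when the PDF was read is an unlikely explanation. Either the screening mark is a slip, or a test that is described nowhere is drawn before written consent.

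**4. Suicide wording.** The 10.1 and synopsis wordings agree with each other. Section 9.2 is shorter and names the same instrument. What is missing is the MINI level that counts as significant.

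**The case against.** The strongest reply is that the 10.1 item points back to 9.2, so the bracket is only a summary and the full list governs. Section 10.1 also treats screening as a preliminary judgement of eligibility. The optional online pre-screen asks about health and medication. Medicines are recorded at W0 before the supplement is handed over, and section 7.4 asks participants to report new treatments so that contraindications can be checked.

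Much of this stands. A reader might infer that ARBs and allergy are never asked about, or that screening fails to implement 9.2. The documents do not support that: the back-reference may bring in the whole list, and the screening form itself is not shown. The back-reference cannot, however, reconcile two different use thresholds. It also introduces a list that repeats nearly every other contraindication, which a screener could reasonably take as complete.

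Three further inferences go too far:

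- **Conflicting suicide rules.** The three wordings can be read as one criterion with its level unstated, which calls for clarification only.
- **No tests behind section 11.1 item a.** That item begins "If any abnormalities are noted from clinical blood tests" and names no tests. Lithium and inflammatory markers including CRP are measured, so there are results to act on. This is missing detail and not a contradiction.
- **A figure for wrongly enrolled participants.** One person in 40 is 2.5%, but that is only a division. Nothing in the protocol estimates how many would be affected.

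**Conclusion.** The point holds as an inconsistency in the eligibility and screening text, in two parts. First, the itemised list in 10.1 omits ARBs and allergy and applies a narrower use threshold than 9.2, with no described re-check at W0. A screener who relies on that list could pass someone whom 9.2 excludes. Second, Table 1 shows a blood test at screening that the screening text does not contain and that would come before written consent.

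The first part assumes that the 10.1 list is used as it stands; if staff work from 9.2 in full, the gap is one of wording. The second part does not depend on that assumption.

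The consequence concerns participant protection and a clear definition of who is enrolled. The sample size of 40, its stated precision and the planned analyses are unaffected. Section 12.2 assesses feasibility by attrition, missed visits and missing mood data, so screen-failure counts are not an outcome. The point is worth correcting because the correction is specific and cheap.

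**What to change.** - The sponsor's clinicians must reconcile section 9.2 with the 10.1 screening list so that both carry the same contraindications, the same drug classes and the same use threshold. Which threshold should stand is for them to decide.
- As a minor clarification, use one wording for the suicide criterion in the synopsis, 9.2 and 10.1, and state the MINI level.
- Either remove the screening mark from the blood-test row of Table 1, or describe that test in 10.1 and 10.2 (what it measures and where it is drawn) and place it after written consent.
- Align any screening form with the reconciled text.

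The cost is protocol wording and, where one exists, a revised form. No analysis or sample-size figure has to be redone.
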